**Table 2– Visit Windows for Immunogenicity Analysis**

Analysis time point label (relative to Day 1)	Scheduled Visit Number	Visit Type	Window of target day* (Day)
[Day 1]	[2]	Vaccination 1, Immunogenicity and Safety	[N/A]
[Day 29]	[3]	Vaccination 2, Immunogenicity and Safety	[+10/-3]
[Day 57]	[4]	Immunogenicity and Safety	[+10/-3]
[Week 28]	[5]	Immunogenicity and Safety	[+7/-7]

\*Relative to Analysis time point

Time windows may be redefined prior to unblinding if the number of samples excluded as per the definitions above are too numerous.

### 5.1.2. Study phases

The phases in the study will be considered as follows:

Phase	# Phase	Period	# Period	Interval	
				From	To
Screening	1			Date and time of signing the informed consent form	One minute prior to start of post-dose period
Post-dose	2	Post- dose 1	1	Date and time of the first vaccination	Minimum of:  a) 23:59 at the date of last contact (for early discontinuation)  b) 23:59 at the database cut- off date for analyses conducted before the final analysis  c) 23:59 on 28 days after the first vaccination (23:59 of day of vaccination + 28 days)  d) One second prior to post- dose 2. If a participant discontinued from the second vaccination, then the maximum of (28 days after the first vaccination at 23:59, scheduled visit 28 days after

					first vaccination at 23:59) will be used
Follow-up 1	3			One minute after Post dose 1 period end	
Minimum of:
 
a) 23:59 at the date of last contact (for early discontinuation)
 
b) 23:59 at the date of database cut-off date in case of interim analysis
 
c) One minute prior to post dose 2

Post-dose	2	Post-dose 2	2	Date and time of the second vaccination	
Minimum of:
 
a) 23:59 at the date of last contact (for early discontinuation)
 
b) 23:59 of day of second vaccination + 28 days

Follow Up 2	4			One minute after Post-dose 2 period end.	
Minimum of:
 
a) 23:59 at the date of last contact (for early discontinuation or participants that completed the study)
 
b) 23:59 at the database cut-off date for analyses conducted before the final analysis

## 5.2. Participant Dispositions

Enrolled participants and reason for screen failures will be summarized overall.

The number of participants in the following disposition categories will be summarized throughout the study by intervention group and overall:

- Participants randomized

- Participants in the FAS
- Participants in the PPII
- Participants in the PPSI
- Participants who discontinued study
- Participants per SARS -CoV-2 vaccination history
- Naïve participants
- Reasons for termination of study
- Previously infected participants (in FAS, PPII and PPSI)

Listings of participants will be provided for the following categories:

- Participants vaccinated and not randomized
- Participants randomized and not vaccinated

### **5.3. Primary Immunogenicity Endpoints Analysis**

#### **5.3.1. Definition of Endpoints**

The primary endpoints are:

- HI titers against each of the 4 influenza vaccine strains at 28 days after the administration of a seasonal quadrivalent *standard-dose* influenza vaccine.
- Antibody GMC by S-ELISA, 28 days after the administration of Ad26.COV2.S vaccine, in the *standard-dose* influenza vaccine groups.

The HAI analysis is based on vaccine specific strains, therefore, for the NI assessment that concerns the *standard dose* of the flu vaccine. The following vaccine-specific strains will be used:

A/Victoria (H1N1)  
A/Cambodia (H3N2)  
B/Victoria (B/Victoria)  
B/Phuket (B/Yamagata)

#### **5.3.2. Analysis Methods**

The NI immunogenicity objectives will be assessed in PPII and PPSI analysis sets by calculating:

- the 2-sided 95% CIs for the difference in log-transformed HI antibody titers against each of the 4 influenza vaccine strains at 28 days after the administration of the seasonal influenza vaccine between the Control and the CoAd group for the standard-dose.

- the 2-sided 95% CIs for the difference in log-transformed S-ELISA titers at 28 days after the administration of Ad26.COV2.S vaccine between the Control and the CoAd group.

For *HI antibody titers* against each of the 4 influenza vaccine strains and for *S-ELISA titers*, an analysis of variance (ANOVA) model will be fitted with the respective titers as dependent variable and group (Control or CoAd), age category (as stratified), previous SARS-CoV-2 vaccination (as collected), and baseline S-ELISA titers as independent variable. The strata will be based on the values in the database for vaccination history (which may differ to the strata as recorded in IWRS).

Based on these ANOVA models, the CIs around the difference will be calculated and will be back transformed (by exponentiation) to CIs around a GMC or GMT ratio (Control group / CoAd group), respectively, and compared to the NI margin of 1.5.

Only if the upper bound of the 2-sided 95% CI for the GMT or GMC ratio (Control group/CoAd group), respectively, of the HI antibody titer for each of the 4 vaccine strains and for S-ELISA lies below 1.5, NI of coadministration versus separate administration will be concluded for both vaccines (seasonal influenza vaccine and Ad26.COV2.S vaccine). If 1 or more confidence limits for the GMC or GMT ratio exceed 1.5 non-inferiority cannot be concluded.

For immunogenicity, baseline is considered as the last assessment pre-vaccination (i.e. it corresponds to Day 1 for CoAd groups or influenza vaccine alone, or to Day 29 for Control groups or Ad26.COV2.S vaccine alone). In a sensitivity analysis, different variances between the groups will be allowed. Therefore, the CIs will be calculated via Welch's ANOVA.

The assessment of the primary endpoints will be performed on individuals who have been previously vaccinated with different types of COVID-19 vaccines. Furthermore, participants may have or not an history of COVID infection. These factors bring a level of variability of immune responses that is unknown.

The populations for analyses related to influenza immunogenicity and COVID-19 immunogenicity are the PPII set and the PPSI set, respectively. The choice of population for the different analyses are described in Section 4.

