1.3. Schedule of Activities

1.3.1. All Participants

Phase	Screening ^a	Treatment Phase ^b					Follow Up ^b		Early termination ^{b,d}
		1	2	Phone Call ^c	3	Phone Call ^c	4	Phone Call	
Clinic Visit #	1			Vac 1	Vac 2	Vac 2	Post Vac 2	Post Vac 2	Exit ^d
Visit Timing		Vac 1 + 7 d		+ 7 d	+ 7 d	+ 28 d	+ 90 d	+ 180 d	
Visit Day/Week	-28 to 1	Day 1	Day 8	Day 29	Day 36	Day 57	Week 16 (3 mo post Vac 2)	Week 28 (6 mo post Vac 2)	
Visit Window		N/A	±3 d	-3/+7 d	±3 d	-3/+7 d	±7 d	±7 d	
Visit Type	Screening	Vaccination, Immunogenicity and Safety	Safety	Vaccination, Immunogenicity and Safety	Safety	Immunogenicity and Safety	Safety	Immunogenicity and Safety	End of Study
Written informed consent ^e	●								
Inclusion/exclusion criteria	●	● ¹							
Demographics	●								
Medical history/prestudy medications	●								
History of SARS CoV 2 vaccination ^f	●								
Physical examinations	●								
Vital signs ^h including body temperature	●	● ²		● ²		●		●	●
Randomization		● ¹							
Pre vaccination check ⁱ		● ¹		● ¹					
Urine pregnancy test ^j	●	● ¹		● ¹					
Humoral Immunity (serum), blood draw, 15 mL		● ¹		● ¹		●		●	● ³
Laboratory assessments: blood draw (whole blood / serum/ plasma), approx. 15 mL ^k		● ¹		● ¹					
Vaccination		●		●					
15 minutes post vaccination observation ^l		●		●					
Solicited AE recording		From Vac 1 +7 d		From Vac 2 +7 d					● ⁴

Phase	Screening ^a	Treatment Phase ^b					Follow Up ^b		Early termination ^{b,d}
Clinic Visit #	1	2	Phone Call ^c	3	Phone Call ^c	4	Phone Call	5	Exit ^d
Visit Timing		Vac 1	Vac 1 + 7 d	Vac 2	Vac 2 + 7 d	Post Vac 2 + 28 d	Post Vac 2 + 90 d	Post Vac 2 + 180 d	
Visit Day/Week	-28 to 1	Day 1	Day 8	Day 29	Day 36	Day 57	Week 16 (3 mo post Vac 2)	Week 28 (6 mo post Vac 2)	
Visit Window		N/A	±3 d	-3/+7 d	±3 d	-3/+7 d	±7 d	±7 d	
Visit Type	Screening	Vaccination, Immunogenicity and Safety	Safety	Vaccination, Immunogenicity and Safety	Safety	Immunogenicity and Safety	Safety	Immunogenicity and Safety	End of Study
Unsolicited AE recording ^m		----- From Vac 1 through Vac 2 +28 d -----							● ⁵
SAE ⁿ and AESI ^o recording		----- Throughout the study -----							●
AEs leading to withdrawal		----- Throughout the study -----							●
COVID 19 recording ^p		----- Throughout the study -----							●
MAAE recording ^q		----- Throughout the study -----							●
Concomitant medications ^r		----- Throughout the study -----							●
Participant diary distribution ^s		●							
Investigator's assessment of reactogenicity ^t			●		●				

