9.4.2. Inferential Endpoints

The NI immunogenicity objectives will be assessed by calculating:

- the 2-sided 95% CIs for the difference in log-transformed HI antibody titers against each of the 4 influenza vaccine strains at 28 days after the administration of the seasonal influenza vaccine between the Control and the CoAd group for the *standard-dose*.
- the 2-sided 95% CIs for the difference in log-transformed S-ELISA titers at 28 days after the administration of Ad26.COV2.S vaccine between the Control and the CoAd group for the *standard-dose*.

For HI antibody titers against each of the 4 influenza vaccine strains and for S-ELISA titers, an analysis of variance (ANOVA) model will be fitted with the respective titers as dependent variable and group (Control or CoAd), age category (as stratified), previous SARS-CoV-2 vaccination (as stratified), and baseline S-ELISA titers as independent variable. Based on these ANOVA models, the CIs around the difference will be calculated and will be back transformed (by exponentiation) to CIs around a GMC or GMT ratio (Control group/CoAd group), respectively, and compared to the NI margin of 1.5.

Only if the upper bound of the 2-sided 95% CI for the GMT or GMC ratio (Control group/CoAd group), respectively, of the HI antibody titer for each of the 4 vaccine strains and for S-ELISA lies below 1.5, NI of co-administration versus separate administration will be concluded for both vaccines (seasonal influenza vaccine and Ad26.COV2.S vaccine). If 1 or more confidence limits for the GMT or GMC ratio exceed 1.5, non-inferiority cannot be concluded.

For immunogenicity, baseline is considered as the last assessment pre-vaccination (ie, it corresponds to Day 1 for CoAd groups or influenza vaccine alone, or to Day 29 for Ad26.COV2.S vaccine). In a sensitivity analysis, different variances between the groups will be allowed. Therefore, the CIs will be calculated via Welch's ANOVA.

The assessment of the primary endpoints will be performed on individuals who have been previously vaccinated with different types of COVID-19 vaccines. This factor brings a level of variability of immune responses that is unknown.

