### Descriptive statistics

To describe the humoral immune response in groups at Day 29 following each vaccination, the following statistics will be calculated for HI antibody titers and S-ELISA titers: N, geometric mean and corresponding 95% CI of the actual values (see below), fold increase from baseline, number of positive samples (definition see below), the number of responders (definition see below), seroprotection, seroconversion.

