#### *Seroconversion*

defined for each of the 4 influenza vaccine strains at 28 days after the administration of a seasonal quadrivalent (*high-dose* and *standard-dose*) influenza vaccine:

- HI titer  $\geq 1:40$  in participants with a pre-vaccination HI titer of  $<1:10$ , or
- a  $\geq 4$ -fold HI titer increase in participants with a pre-vaccination HI titer of  $\geq 1:10$ .

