## **6.2. Appendix 2 Changes to Protocol-Planned Analyses**

For HI antibody titers against each of the 4 influenza vaccine strains and for S-ELISA titers, an analysis of variance (ANOVA) model will be fitted with the respective titers as dependent variable and group (Control or CoAd), age category (as stratified), previous SARS-CoV-2 vaccination (as collected), and baseline S-ELISA titers as independent variable.

The strata will be based on the values in the database for vaccination history (which may differ to the strata as recorded in IWRS).

In order to evaluate the cross-reactivity between HAs, we will analyze the HI responses to mis/unmatched vaccine strains. This analysis will be performed in a subset of participants, namely, study participants that are 65 yo and older. Samples will be tested specifically for the H3N2 and the B/Victoria influenza strains. Participants corresponding to Groups 1 and 2 will be analyzed for the following non-matched strains: A/Tasmania and B/Washington. Participants corresponding to Groups 3 and 4 will be analyzed for the following non-matched strains: A/Cambodia and B/Victoria.

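### The four primary HI models adjust for baseline S-ELISA but not for the same strain's Day 1 HI titer, giving up precision that costs almost nothing to recover

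*SAP*

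**What the plan says.** SAP 5.3.2 specifies an ANOVA for each HI strain and for S-ELISA, with group, "age category (as stratified), previous SARS-CoV-2 vaccination (as collected), and baseline S-ELISA titers as independent variable". SAP Appendix 2 repeats the list and applies it to both kinds of endpoint: "For HI antibody titers against each of the 4 influenza vaccine strains and for S-ELISA titers". Protocol 9.4.2 has the same list except for the source of the vaccination stratum: "age category (as stratified), previous SARS-CoV-2 vaccination (as stratified), and baseline S-ELISA titers as independent variable". The Welch sensitivity analysis adds no HI baseline.

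The Day 1 HI titer will exist for another purpose. The Schedule of Activities (protocol 1.3.1) has the row "Humoral Immunity (serum), blood draw, 15 mL" marked as pre-vaccination on Day 1. Seroconversion in SAP 5.3.2 is defined by thresholds applied "in participants with a pre-vaccination HI titer of" a given level. The descriptive statistics for HI and S-ELISA include "fold increase from baseline, number of positive samples".

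The two documents define baseline differently. In protocol 9.4.2 "it corresponds to Day 1 for CoAd groups or influenza vaccine alone, or to Day 29 for Ad26.COV2.S vaccine", so it follows the vaccine. SAP 5.3.2 ends instead with "or to Day 29 for Control groups or Ad26.COV2.S vaccine alone", which brings in the study arm.

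**The concern.** The plan accepts adjustment for a baseline titer in principle, but gives the outcome's own baseline only to the S-ELISA model. The HI models receive the antibody level to a different pathogen. Pre-existing HI titer is a natural predictor of post-vaccination HI titer, and leaving it out keeps its variance in the residual.

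This matters because success requires all five upper limits to lie below 1.5, and four of the five tests are affected. Chance imbalance in prior influenza immunity between Groups 1 and 2 also stays unadjusted. Under randomization the confidence interval already allows for that imbalance, but at the price of being wider than it need be.

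The baseline wording is a smaller, separate point. For a Control participant the SAP could be read as putting the Day 29 S-ELISA sample into the HI model. That sample is taken after the influenza vaccination, at the HI endpoint visit, whereas the co-administration arm would use Day 1.

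**Working it through.** **Inputs.**
- HI SD 0.53 and S-ELISA SD 0.50 on the log10 scale, margin 1.5, two-sided 95% CI, true ratio 1, 305 per group (protocol 9.2, SAP 3).
- Allowance of about 30 per group for exclusions, drop-outs and missing samples (SAP 3), so 305 − 30 = 275 evaluable.
- r is the partial correlation of Day 1 and Day 29 log HI given the covariates already in the model. The documents do not give it, so a range is shown.
- 0.53 is treated as the residual SD under the planned model. The documents do not say whether it is raw or residual.

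**Formulas.** The margin is log10(1.5) = 0.1761. SE = SD × √(2/n) × √(1 − r²). Power is from the noncentral t with 2n − 2 degrees of freedom and noncentrality 0.1761/SE. Five-test power under independence is (HI power)⁴ × S-ELISA power. The largest observed Control/CoAd ratio that still passes is 10^(0.1761 − t × SE).

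**The plan's own figure.** With r = 0 and n = 275, SE = 0.53 × √(2/275) = 0.0452 and power is 97.31%. At n = 278 it is 97.44% and at n = 279 it is 97.49%, so the stated 97.45% is reproduced without the extra covariate.

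**Effect of adding Day 1 HI, n = 275 per group, S-ELISA power 98.47%.**

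| r | Per-strain power | Five-test power (independence) | Largest passing ratio |
|---|---|---|---|
| 0 | 97.31% | 88.3% | 1.223 |
| 0.1 | 97.43% | 88.7% | 1.224 |
| 0.3 | 98.29% | 91.9% | 1.234 |
| 0.5 | 99.43% | 96.2% | 1.257 |
| 0.7 | 99.98% | 98.4% | 1.296 |

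For example, at r = 0.3, SE = 0.0452 × √(1 − 0.09) = 0.0431, and 0.9829⁴ × 0.9847 = 0.919.

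**Sensitivity to the other assumptions.**
- All 305 per group evaluable: five-test power is 92.8% (r = 0), 95.3% (0.3), 98.0% (0.5).
- S-ELISA variance also reduced by its own baseline, assumed correlation 0.5, n = 275: 89.5%, 93.1%, 97.5%.
- Common correlation of 0.5 assumed among the four HI tests, S-ELISA independent, n = 275: about 90.3%, 93.0%, 96.5%.
- True ratio 1.1 in all four strains (illustration, normal approximation, independence, n = 275): 50.5%, 58.5%, 73.9%.

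**Sample-size equivalent.** The residual variance falls by r², that is 9%, 25% and 49% at r = 0.3, 0.5 and 0.7. The evaluable number per group for 97.45% per strain falls from 278 to 253, 208 and 142.

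**The case against.** The planned model is valid, prespecified and meets its stated per-strain power, so nothing in the plan fails without the extra covariate. The benefit rests on an r that the documents do not supply, and even at r = 0.3 the largest passing ratio moves only from 1.223 to 1.234. If many Day 1 titers fall below the LLOQ and are set to LLOQ/2, the covariate carries less information.

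The base case is also unfavourable to the plan. The four HI titers come from the same people, so their tests are probably positively correlated. With an assumed correlation of 0.5, five-test power already exceeds 90% without the covariate, and the gain at r = 0.3 is 2.7 points rather than 3.6. The PPII set admits vaccine-naïve participants (SAP 4), so the HI models may have more than 275 per group. If 0.53 is a raw SD, starting power is understated.

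These points are fair and they shrink the gain without removing it. At r = 0.5 the correlated-test case still rises from about 90.3% to 96.5%. None of them is a reason to leave out a covariate already in hand. Two practical objections also stand. A participant without a Day 1 HI result would leave that strain's model, because SAP 5.3.3 does not impute missing data. A protocol amendment is not essential, because SAP Appendix 2 already records departures from the protocol's analyses.

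On the baseline wording, Control receives no Ad26.COV2.S before Day 29, so neither candidate S-ELISA sample carries an effect of that vaccine. The ambiguity remains, but it adds nothing to the size of the main point.

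**Conclusion.** The concern holds as lost efficiency on four of the five tests that must all pass. The planned analysis remains unbiased with correct type I error, and the stated 97.45% per strain is not disputed. At 275 evaluable per group, true ratio 1 and independent tests, five-test power would rise from 88.3% to 91.9% at r = 0.3 and 96.2% at r = 0.5. The gain is negligible at r = 0.1 and becomes material from about 0.3. It is smaller if the strain tests are positively correlated or if more participants enter the HI models. Confidence is high that the covariate is omitted and available; the size of the benefit is conditional on r. The 88.3% is not offered as a contradiction of the plan's overall power of at least 90%, because positive correlation or a larger evaluable number would lift it above that.

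**What to change.** Before unblinding, amend SAP 5.3.2 and record the change in SAP Appendix 2 (and align protocol 9.4.2 if the protocol is amended):

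- Add to each HI model the log-transformed Day 1 HI titer for the same strain, in both arms. State that values below the LLOQ follow the LLOQ/2 rule of SAP 5.3.3.
- Keep baseline S-ELISA in the S-ELISA model, where it is needed. If it also stays in the HI models, specify the Day 1 sample in both arms.
- Report, by strain and arm, how many participants leave the HI model for want of a Day 1 HI titer.

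The cost is a few lines of SAP text, one added variable in the program and one degree of freedom per HI model. No new samples, visits or participants are needed.

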### Descriptive statistics

To describe the humoral immune response in groups at Day 29 following each vaccination, the following statistics will be calculated for HI antibody titers and S-ELISA titers: N, geometric mean and corresponding 95% CI of the actual values (see below), fold increase from baseline, number of positive samples (definition see below), the number of responders (definition see below), seroprotection, seroconversion.

#### *Geometric mean and 95% CI*

For the calculation of the geometric mean and its 95% confidence interval (CI), we assume that the  $\log_2$  and  $\log_{10}$  transformed values of HI antibody and S-ELISA concentrations respectively are normally distributed. Therefore, the calculation of the geometric mean and the corresponding 95%

CI will be done in the following way: (1) the arithmetic mean and its corresponding 95% CI (using the t-distribution) are calculated on the  $\log_2$  and  $\log_{10}$  transformed values of concentration; (2) these values are back transformed to provide the geometric mean and its corresponding 95% CI concentration.

#### *Positive Sample*

A sample will be considered positive if the value is strictly greater than the LLOQ ( $>\text{LLOQ}$ ).

#### *Responder*

A post-baseline sample will be considered a responder if at least one of the following conditions is satisfied:

- The baseline sample value is less than or equal to the LLOQ ( $\leq\text{LLOQ}$ ) and the post-baseline sample is strictly greater than the LLOQ ( $>\text{LLOQ}$ )
- The baseline sample value is strictly greater than the LLOQ ( $>\text{LLOQ}$ ) and the post-baseline sample value represents an at least 4-fold ( $\geq 4$ -fold) increase from the baseline sample value.

#### *Seroconversion*

defined for each of the 4 influenza vaccine strains at 28 days after the administration of a seasonal quadrivalent (*high-dose* and *standard-dose*) influenza vaccine:

- HI titer  $\geq 1:40$  in participants with a pre-vaccination HI titer of  $<1:10$ , or
- a  $\geq 4$ -fold HI titer increase in participants with a pre-vaccination HI titer of  $\geq 1:10$ .

#### *Seroprotection*

defined for each of the 4 influenza vaccine strains as HI titer  $\geq 1:40$  at 28 days after the administration of a seasonal quadrivalent (*high-dose* and *standard-dose*) influenza vaccine.

### **5.3.3. Handling of Missing and/or Unquantifiable Immune Response Data**

Missing immune response data will not be imputed.

Values below the lower limit of quantification (LLOQ) will be imputed based on the type of analysis:

- Values below LLOQ will be imputed to  $\text{LLOQ}/2$ , except for the calculation of the geometric mean of the increase from baseline where values below LLOQ will be imputed to LLOQ.

- Values above the upper limit of quantification (ULOQ) or Max Range will be imputed with the ULOQ / Max Range.

The ULOQ / Max Range and LLOQ values per assay will be available in the database.

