9.2. Sample Size Determination

Sample size calculations are performed under the following assumptions:

- no effect of co-administration of Ad26.COV2.S vaccine and seasonal influenza vaccine on the immune response against influenza as measured by HI antibody titers against the 4 influenza vaccine strains at 28 days after the administration of seasonal influenza vaccine
- the use of Afluria Quadrivalent for *standard-dose* (adults ≥ 18 to < 64 years of age and older adults ≥ 65 years of age)
- a standard deviation of 0.53 for the *standard-dose* at the \log_{10} scale for HI antibody titers against the 4 influenza vaccine strains at 28 days after the administration of seasonal influenza vaccine (with or without Ad26.COV2.S)
- no effect of co-administration of Ad26.COV2.S vaccine and seasonal influenza vaccine on the immune response against SARS-CoV-2 as measured by S-ELISA at 28 days after the administration of Ad26.COV2.S vaccine
- a standard deviation of 0.50 at the \log_{10} scale for S-ELISA at 28 days after the administration of Ad26.COV2.S vaccine (with or without seasonal influenza vaccine)
- a NI margin of 1.5
- 2-sided α of 5%

A total of approximately 305 (*standard-dose*) participants per group (total N 610) who have completed a primary COVID-19 vaccine series are needed to have 97.45% power to show NI in HI antibody titers for 1 influenza vaccine strain.

The sample size accounts for exclusions from the per protocol set (see Section 9.3), drop-outs and missing samples.

With this sample size, the overall power to show NI in HI antibody titers against each of the 4 influenza vaccine strains at 28 days after the administration of seasonal influenza vaccine as well as NI in S-ELISA at 28 days after the administration of Ad26.COV2.S vaccine is at least 90%.

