### 3. SAMPLE SIZE DETERMINATION

Sample size calculations are performed under the following assumptions:

- no effect of coadministration of Ad26.COV2.S vaccine and seasonal influenza vaccine on the immune response against influenza as measured by HI antibody titers against the 4 influenza vaccine strains at 28 days after the administration of seasonal influenza vaccine
- the use of Afluria Quadrivalent for *standard-dose* (adults  $\geq 18$  to  $<64$  years of age and older adults  $\geq 65$  years of age)
- a standard deviation of between 0.53 for the *standard-dose* at the  $\log_{10}$  scale for HI antibody titers against the 4 influenza vaccine strains at 28 days after the administration of seasonal influenza vaccine (with or without Ad26.COV2.S)
- no effect of coadministration of Ad26.COV2.S vaccine and seasonal influenza vaccine on the immune response against SARS-CoV-2 as measured by S-ELISA at 28 days after the administration of Ad26.COV2.S vaccine
- a standard deviation of 0.50 at the  $\log_{10}$  scale for S-ELISA at 28 days after the administration of Ad26.COV2.S vaccine (with or without seasonal influenza vaccine)
- Log transformed ( $\log_{10}$  scale) immune response data are normally distributed
- a non-inferiority margin of 1.5
- 2-sided  $\alpha$  of 5%

A total of approximately 305 (*standard-dose*) participants per group are needed to have 97.45% power to show non-inferiority in HI antibody titers for each influenza vaccine strain.

The sample size accounts for exclusions from the per protocol set, drop-outs and missing samples resulting in a total sample size up to approximately 610 participants who have completed a primary COVID-19 vaccine series. The N margin was  $\sim 10\%$  ( $\sim 30$  per group).

With this sample size, the overall power to show NI in HI antibody titers against each of the 4 influenza vaccine strains at 28 days after the administration of seasonal influenza vaccine as well as NI in S-ELISA at 28 days after the administration of Ad26.COV2.S vaccine is at least 90%.

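### Setting titers above the ULOQ to the ULOQ in the primary ANOVAs can raise the false non-inferiority rate if a material share of values is capped, and no planned analysis would show it.

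*SAP*

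**What the plan says.** SAP 5.3.3 sets the rule for high readings: "Values above the upper limit of quantification (ULOQ) or Max Range will be imputed with the ULOQ / Max Range". The exception in that section, for the geometric mean increase from baseline, concerns only values below the LLOQ. On the limits themselves it says: "The ULOQ / Max Range and LLOQ values per assay will be available in the database". Neither document gives a numerical ULOQ or an expected share of samples above one.

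SAP 5.3.2 fits an ANOVA to each of the four HI titers and to S-ELISA, with group, age category, previous COVID-19 vaccination and baseline S-ELISA as terms. The interval for the Control/CoAd ratio is back-transformed and "compared to the NI margin of 1.5". The model has no term for censoring.

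The only alternative model is Welch's ANOVA, for unequal variances. SAP 4 and 5.1.1 also allow FAS tables and out-of-window visits as sensitivity analyses. All of these would use the same capped values. SAP 3 assumes that log10-transformed "immune response data are normally distributed", and Protocol 9.2 assumes the same SD with or without co-administration.

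**The concern.** A value above the ULOQ is right-censored: it is known only to exceed the limit. Suppose co-administration lowers the response and the two groups have similar spread. Then more Control than CoAd values reach the ceiling. Replacing them with the ceiling removes part of the real Control advantage and also reduces the SD. In a non-inferiority trial both effects work toward declaring success.

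S-ELISA is the endpoint where high values are most plausible. The PPSI set is restricted to people with a completed primary series, previously infected participants are kept, and everyone receives a further spike dose before the endpoint sample. If capping were common, a non-inferiority claim could rest partly on the assay ceiling, and no planned re-analysis would separate the two.

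**Working it through.** **Inputs.** The margin is 1.5 (SAP 3), so δ = log10(1.5) = 0.1761. The log10 SD is 0.50 for S-ELISA and 0.53 for HI, equal in both groups (Protocol 9.2). Two-sided alpha is 5%, so 2.5% for the non-inferiority decision. Evaluable n per group is 305 − 30 = 275 (SAP 3). The share of Control values above the ULOQ is not in the documents and is *assumed*, from 0% to 30%.

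**Reproducing the plan's figure.** Power for one HI strain at a true ratio of 1 is Φ(δ / (SD·√(2/n)) − 1.96). With SD 0.53 and n = 275 this is Φ(3.896 − 1.96) = 97.36%; with n = 277 it is 97.44%. The stated figure is 97.45%, so the set-up matches.

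**Effect of capping.** Place the Control mean at 0 and the CoAd mean at −δ, so that the true ratio is exactly 1.5. Let U be the ULOQ on the log10 scale. For X normal with mean μ and SD σ, with a = (U − μ)/σ:

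- E[min(X,U)] = μΦ(a) − σφ(a) + U(1 − Φ(a))
- E[min(X,U)²] = (μ² + σ²)Φ(a) − σ(μ + U)φ(a) + U²(1 − Φ(a))

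Let d be the difference of the capped means and SE = √((v₁ + v₂)/n), where v₁ and v₂ are the capped variances. The false non-inferiority rate is Φ((δ − d)/SE − 1.96).

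*Worked case: σ = 0.50, 10% of Control capped.*

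- U = 1.2816 × 0.50 = 0.6408.
- Control: mean −0.0237, variance 0.2093.
- CoAd: a = 1.634, so 5.1% is capped; mean −0.1868, variance 0.2283.
- d = 0.1631, an expected ratio of 10^0.1631 = 1.456.
- SE = √(0.4376/275) = 0.0399, against 0.0426 uncapped.
- Rate = Φ((0.1761 − 0.1631)/0.0399 − 1.96) = Φ(−1.636) = 5.1%.

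| Control above ULOQ (assumed) | Expected ratio, SD 0.50 | False NI, SD 0.50 | False NI, SD 0.53 |
|---|---|---|---|
| 0% | 1.500 | 2.5% | 2.5% |
| 2% | 1.492 | 2.8% | 2.8% |
| 5% | 1.479 | 3.5% | 3.5% |
| 10% | 1.456 | 5.1% | 5.0% |
| 20% | 1.408 | 11.1% | 10.6% |
| 30% | 1.359 | 24% | 22.5% |

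**Simulation check.** Linear-model simulation (20,000 runs, SD 0.50) gave 3.5%, 4.9% and 10.9% at 5%, 10% and 20% capped. Adding a baseline covariate with an assumed correlation of 0.5 gave 3.8%, 5.4% and 12.9%, so covariate adjustment does not remove the effect.

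**Study level.** Success needs all five endpoints. Take S-ELISA at 1.5 and four independent, uncapped HI strains with no true difference. The rate is then multiplied by 0.9736⁴ = 0.898: 2.25% with no capping, 4.6% at 10% and 10.0% at 20%.

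**Unequal SDs** (Control 0.50, true ratio 1.5, at 5%, 10% and 20% of Control capped):

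- CoAd SD 0.60: 2.3%, 2.5%, 3.4%.
- CoAd SD 0.70: 1.3%, 0.9%, 0.7%.

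**Censored model.** A right-censored normal likelihood with common SD (3,000 simulated trials per setting, Monte Carlo standard error about 0.3 points) gave false non-inferiority of 3.0% (SD 0.50, 10% capped), 2.1% (SD 0.50, 20%), 3.0% (SD 0.53, 5%) and 2.5% (SD 0.53, 10%). Estimated ratios were 1.496 to 1.505.

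**The case against.** The strongest reply is that nothing in the documents shows that any sample will exceed the ULOQ. High titers are not the same as titers above the assay range, and that range is not given. Exclusion criterion 12.1 keeps out anyone vaccinated against SARS-CoV-2 in the six months before the first study vaccination, which limits baseline titers. Protocol 8 refers to a laboratory manual, not available here, which could provide for re-dilution; its absence from the SAP proves little. All of this stands, and it is why the figures are conditional.

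The direction also depends on similar SDs. SAP 5.3.2 calls the variability arising from mixed vaccination and infection histories unknown and plans Welch's ANOVA. A clearly more variable CoAd group would make capping neutral or conservative. That stands too, although equal SDs are the plan's own assumption.

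The censored model is not free of assumptions. In a small simulation (800 runs, common SD fitted, 20% capped) it gave a ratio of 1.46 and about 5% false non-inferiority when the CoAd SD was 0.40, and 1.54 and about 1% when it was 0.60. This argues for a version with group-specific variances, and against making the censored model primary.

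Finally, the dot-plots and reverse distribution curves in SAP 5.4.1.2 would show a pile-up at the ceiling. They would reveal capping but not its effect on the non-inferiority decision.

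**Conclusion.** The point holds as a conditional one. The capping rule feeds directly into the primary non-inferiority models, and no planned sensitivity analysis removes it. The false non-inferiority rate rises when a material share of values is capped, the true ratio is at or above 1.5 and the SDs are similar. Under normal log10 titers, common SD 0.50 and 275 per group, the effect is negligible up to about 2% of Control values capped, roughly doubles the error at 10%, and reaches about 11% at 20%. These rates are per endpoint.

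A reader might infer that the rule inflates the error in this trial whatever the data, or that the 20% to 30% rows describe what will happen. The documents support neither. They give no ULOQ and no share above it. With nothing capped the rate is unchanged, and under the plan's scenario of no co-administration effect with equal SDs the ratio stays at 1. A reader might also conclude that the primary model must be replaced, or switched once some share is exceeded. The evidence does not require that, and a data-dependent switch would bring its own problem.

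**What to change.** In SAP 5.3.2 and 5.3.3, before unblinding:

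1. Tabulate the number and share of values above the ULOQ / Max Range by group for each of the five primary endpoints.
2. For every primary endpoint with any value above the ULOQ, pre-specify as a sensitivity analysis a normal model right-censored at that limit. It should use the same covariates as the ANOVA, with a second version allowing group-specific variances.
3. State that a non-inferiority conclusion is reported as robust only if the censored-model upper 95% limit for Control/CoAd is also below 1.5.

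Leave unchanged the primary ANOVA, the LLOQ/2 rule, and substitution for descriptive GMTs. Do not add a trigger that switches the primary model according to the data.

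The cost is SAP wording and a little extra model fitting per endpoint. The added analysis relies on log-normality in the unobserved upper tail, which SAP 3 already assumes, and its interval is slightly wider when values are censored. Where nothing is capped, it returns the ANOVA estimate.
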